#### **Study Procedures:**

Subjects with complaints of back pain will be recruited from Columbia University Student Health and from Columbia Doctors Physical Medicine and Rehabilitation practice. Subjects will be consented and randomized to either the UPRIGHT device group or control group. The UPRIGHT group will get a brief training on how to use the device. This will involve downloading the app on subjects phone. We will set

up a separate de-identified gmail account which will be used collect data from the device. They will be instructed on how and where to attach the device to their back. The subject will be asked to sit with proper posture in a chair without leaning against the back rest with both feet flat on the ground. The training is once daily and each day the time increase according to the provided training protocol. The subjects will wear the device once per day for 4 weeks.

The subject needs to use a new adhesive (which will be provided) each time they put the device on. The device will be calibrated to detect changes in posture. A detailed physical exam as well as medical history, family history will be conducted on all participants. Subjects will then be given a 4 week training protocol through the app. The control group will have a 15 minute instruction on proper posture and an ergonomic handout explaining how to sit and stand with proper posture.

At the end of 4 weeks subjects will be contacted via telephone to complete a questionnaire to assess their current pain level, perception of posture, and satisfaction with the device. At the end of 4 weeks participants in the control group will be given an UPRIGHT device if they continue to have pain.

Prior to recruitment we will pilot the use of this device with 5 healthy controls. The purpose of the pilot study is to assess for any difficulties we may encounter with the device and while training with the device.

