### **Research Question(s)/Hypothesis(es):**

The purpose of the this study is to determine if patients with back pain who use a device that provides a proprioceptive reminder regarding posture (UPRIGHT device) demonstrate improved pain control and self perception of posture over those who receive a brief instruction on posture and an ergonomic handout.

Hypothesis: There will be no difference in back pain score or self perception of posture between those using the UPRIGHT device and those receiving posture/ergonomic instruction alone.

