### **Scientific Abstract:**

Back pain is one of the most common conditions among the adult population (1). There is evidence that individuals with back pain have impaired motor control of trunk muscles and delayed neuromuscular recruitment (2,3). Poor posture has been associated with spinal extensor weakness, back pain, and lower quality of life scores (4). Those who spend prolonged time sitting in poor posture often develop muscular imbalances leading to tight chest muscles and weakness in back muscles. Back pain is commonly treated with flexibility and strengthening and exercises as well and a health education regarding proper posture (5). The purpose of the this study is to determine if patients with back pain who use a device that provides a proprioceptive reminder regarding posture (UPRIGHT device) demonstrate improved pain control and self perception of posture over those who receive a brief instruction on posture and an ergonomic handout.

Hypothesis: There will be no difference in back pain score or self perception of posture between those using the UPRIGHT device and those receiving posture/ergonomic instruction alone. This is a randomized controlled study to determine if patients between the ages of 18-50, with posture related low back pain, who use the UPRIGHT device demonstrate improved pain control and self perception of posture compared to those given standard ergonomic instruction. Subjects will complete a baseline history, physical exam and questionnaire to assess current pain level.

Subjects will be randomized into two groups. One group will receive the UPRIGHT device and a 15 minute tutorial on using the device. Subjects will complete a 4 week training program using the device. The control group will receive a 15 minute instruction on proper posture and an ergonomic handout explaining how to sit and stand with proper posture. At the end of 4 weeks subjects will be contacted via telephone to complete a questionnaire to assess their current pain level, perception of posture, and satisfaction with the device.

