#### **Study Population:**

A total of up to 45 participants will be enrolled into this study with a target accrual of 35 participants treated.

This study consists of two groups:

1. Upright posture device x 4 weeks.
2. Ergonomic instruction (15-20 min) and handout.

The Inclusion Criteria is as follows:

1. Ages 18-50
2. Postural related back pain

The Exclusion Criteria is as follows:

1. A diagnosis of significant scoliosis, herniated/bulging disc, lumbar spondylolysis, radiculitis, facet arthrosis, fibromyalgia, rheumatoid arthritis, seronegative spondyloarthropathy
2. Neurologic deficits on exam
3. Currently in PT

The participants will fall in either one of the following Intervention /exposure groups: Group 1- Upright device training x 4 weeks Group 2- Ergonomic training 30 min, ergonomic handout. The control group will get the upright device if they still have pain.

Randomization will be done by research member not in contact with participant using [www.randomization.com](http://www.randomization.com) and will use 3 blocks of 10 for randomization. At the end of 4 weeks patient will be reassessed with visual analog pain scale, and self perception posture scale. Patients receiving the upright device will have a brief training on the use of the device and proper posture. They will use a training protocol (attached). The control group will have a 15-20 minute instruction on proper posture and an ergonomic handout.

Patients will be identified by a physician at student health and enrolled by the research team. Informed consent will be obtained.

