**Statistical Plan:**

No power analysis will be done, as only one other study has been published using this device. We'll be using 30 participants, as this study had 30 subjects participating in study.

For within subjects, data will be analyzed using paired T-test analysis. For between subjects data will be analyzed using ANOVA. Currently there are no similar studies to determine the sample size, we plan to analyze the outcomes.

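### Week-4 outcomes come from one telephone contact and the named tests use only people reached; non-response tied to arm and pain could bias the comparison in either direction

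*Combined protocol and SAP*

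**What the plan says.** The hypothesis names two outcomes: "There will be no difference in back pain score or self perception of posture between those using the UPRIGHT device" (Research Question(s)/Hypothesis(es)). Study Population gives the instruments and time point: "At the end of 4 weeks patient will be reassessed with visual analog pain scale, and self perception posture scale". Study Procedures gives the mode: "At the end of 4 weeks subjects will be contacted via telephone to complete a questionnaire to assess their current pain level". The Scientific Abstract also describes a telephone questionnaire at week 4. No later or intermediate outcome assessment appears, and nothing is said about number of call attempts, a time window or a second contact route.

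The analysis, under Statistical Plan, is: "For within subjects, data will be analyzed using paired T-test analysis. For between subjects data will be analyzed using ANOVA". No analysis set, missing-data rule or sensitivity analysis is given.

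Two features differ by arm. On the control side, "participants in the control group will be given an UPRIGHT device if they continue to have pain", at the end of the four weeks. On the device side, "The training is once daily and each day the time increase according to the provided training protocol", with a fresh adhesive for each use (both Study Procedures).

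At baseline, "Subjects will complete a baseline history, physical exam and questionnaire to assess current pain level" (Scientific Abstract). No baseline posture score is named.

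**The concern.** A between-arm test answers the trial's question only if the people analysed represent the people randomised. Here a person not reached at week 4 has no outcome at all, and neither named test can include them.

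The protocol contains plausible reasons for the loss to be related to both arm and pain. A control still in pain has something to gain from the week-4 contact, and a pain-free control has less. A device user who gave up the daily sessions without benefit may be harder to reach. Both would lower the pain seen among device-arm responders relative to control responders. Opposite patterns are also plausible (see the objection). With about 15 people per arm, a few selective losses matter, and the plan has no step to limit the loss or to show whether the conclusion survives it.

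**Working it through.** **Nothing to reproduce.** The plan gives no power calculation, SD, alpha or loss rate. Only the count can be checked: 3 blocks of 10 = 30, or 15 per arm if allocation is 1:1 (the ratio is not stated).

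**Assumptions for illustration.** 15 per arm; no true effect; week-4 pain standard normal in both arms; ANOVA applied to week-4 values; two-sided 5% test; 20% loss in each arm unless stated; baseline to week-4 correlation 0.5 where baseline is used. The log-odds of being missed change linearly with pain, and the slope is given per SD.

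**Formula for the bias.** In one arm, responder mean minus true mean = −(loss) × (mean of missing − mean of responders). With 20% loss and a slope of 1, those missed average about 0.86 SD more pain than responders, so the shift is −0.20 × 0.86 = −0.17 SD. If the other arm has the opposite slope, the difference between arms is 2 × −0.17 = −0.34 SD.

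**Simulation of ANOVA among responders** (20,000 or 40,000 trials per scenario; negative values favour the device):

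| Non-response pattern | Bias (SD) | False positives |
|---|---|---|
| 20%, unrelated to pain | 0.00 | 5.0% |
| 20%, slope 1 in both arms, same direction | 0.00 | 5.1% |
| 20%, slope 1 in one arm only | −0.17 to −0.18 | 7% |
| 20%, slopes +0.5 device, −0.5 control | −0.19 | 7.5% |
| 20%, slopes +1 device, −1 control | −0.35 | 13.5% |
| 20%, slopes −1 device, +1 control | +0.35 | 13.6% |
| 10%, slopes +1 device, −1 control | −0.18 | 7.6% |
| 30%, slopes +1 device, −1 control | −0.51 | 21.3% |

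**What baseline adjustment does.** If non-response depends on baseline pain only (slopes +1 and −1), ANOVA is biased by −0.18 SD (7.2% false positives). The baseline-adjusted comparison is unbiased (−0.003 SD, 5.1%). If selection acts on week-4 pain itself (slopes +1 and −1), adjustment leaves −0.27 SD and 11.2%. The large-sample ratio of standard errors is √(1 − 0.5²) = 0.87. At this sample size the gain is about 10%.

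**What imputation does.** In that last scenario, imputing week-4 pain from baseline within arm gave −0.267 SD, the same as the adjusted analysis of responders. With one follow-up and baseline as the only predictor, it adds essentially nothing.

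**Precision.** The 95% half-width is t × √(2/n). With 15 per arm it is t(28) × √(2/15) = 0.75 SD. With 12 per arm (15 × 0.8) it is t(22) × √(2/12) = 0.85 SD.

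**The case against.** A reader might infer that non-response is likely and will favour the device. The documents do not support that. They give no loss rate and nothing on who would be missed. The reverse is arguable: controls given only instruction and a handout, and still in pain, may disengage, while dissatisfied device users may welcome a call that asks about satisfaction. The reversed pattern biases by the same amount against the device, and equal pain-related loss causes no bias. The control-arm mechanism also needs participants to know beforehand that continuing pain brings a device. Consent pages are not available, so this cannot be checked. This objection stands, and it limits the point to a possible bias of unknown sign.

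A reader might also take "A total of up to 45 participants will be enrolled into this study with a target accrual of 35 participants treated" (Study Population) as a planned loss of (45 − 35)/45 = 22%. The text contrasts enrolled with treated and does not mention people missed at week 4, so the 20% used here is purely an assumption.

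It can fairly be said that complete-case analysis is never stated, that repeat calls are not excluded, and that Study Population names the scales without a mode. These are inferences from silence. Even so, no text points to another route or another handling of missing values, and the named tests cannot use a person without a week-4 value.

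Finally, 0.35 SD needs steep and opposite selection in both arms, and the milder cases raise the false-positive rate only to about 7%. That is correct, and the verdict gives the range. The mechanism is also clearer for pain than for posture perception.

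**Conclusion.** The point holds as a weakness in follow-up and analysis, not as a demonstrated bias toward the device. Both outcomes depend on one week-4 contact, the named tests use only those with a value, and the design gives reasons why response could depend on arm and pain.

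Under the assumptions above, the bias at 20% loss runs from nil (equal selection), through about 0.2 SD (half-strength opposite selection, or one arm only), to about 0.35 SD in either direction (strong opposite selection). False positives run from 5% to about 13%. The loss rate, selection strength and correlation are all assumed. Extra enrolment would restore precision but would not remove this bias. The change is worth making because values not sought at week 4 cannot be recovered later.

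**What to change.** **Study Procedures.** Seek the week-4 questionnaire from every randomised participant, whether or not they still use the device, in the same window for both arms. State a fixed minimum number of call attempts, followed by the same questions through a text or e-mail link. Report response and reasons for non-response by arm.

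**Statistical Plan.** Replace the unadjusted ANOVA for pain with a comparison by randomised arm adjusted for baseline pain, which the trial already collects. Say plainly that this deals with loss related to baseline pain and improves precision, but does not remove selection on week-4 pain. Do the same for posture only if a baseline posture score is collected. Imputation from baseline alone is not needed.

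If any week-4 values are missing, add one pre-stated sensitivity analysis that shifts missing values in each arm separately and in both directions, and report where the conclusion changes. Worsening only the device arm would mislead: with 20% loss and equal selection, a 1 SD shift there alone creates 0.20 × 1 = 0.20 SD of bias against the device.

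**Cost.** Some extra calls, one online copy of the questionnaire and a few sentences, for about 30 people. The downside is a little more staff time and a sensitivity result that may be less favourable.

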**Recruitment:**

Patients will be identified by a physician at student health or by a Columbia Doctors PM&R physician who will first introduce the study to the patients and enrolled by the research team. Informed consent will be obtained. Subjects who presents to the Columbia Health Clinic or Columbia Doctors Rehabilitation Medicine with complaints of back pain who meet the criteria will be asked to participate in our study. Information about the study will be provided and if they choose to participate they will be consented by our research coordinator. They will then be scheduled for study assessments. This study is completely voluntary. None of residents, students, fellows or employees within our Rehabilitation Department will be asked to participate in this study. Recruitment flyers will also be placed in the Department of Rehab at CUMC as well as displayed at student health at Columbia University.

An electronic flyer (attached) will be sent to the graduate school of arts and sciences communication department for them to attach to their monthly newsletter sent to the graduate students on our behalf. The communication department will not give us their list serve at any time. Graduate students are added to this list serve when registered for graduate classes at Columbia University and the communications department is the sole owner of this list. An individual who wants to participate in the study will contact [name] directly and no one from the communication department will ever see this information.

[name], an employee of Upright, will send out the attached email (Upright\_email script) to individuals who have purchased an Upright device in the past on our behalf. We will never have access to these individuals' contact information or listserve. When someone purchases an Upright device they are added onto their mailing listserve and agree to receive emails from Upright. [name] and Upright will be sending the email referencing our study and provide our contact information. An individual who wants to participate in the study will contact [name] directly and no one from Upright will ever see this information.

**Title:** Upright Back Posture Device Study (AAAR4123)

**NCT:** NCT03769246

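### Past buyers of the Upright device are recruited and not excluded, so device owners can be randomised to control with no stated bar on, or record of, own-device use

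*Combined protocol and SAP*

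**What the plan says.** Under Recruitment, besides the two clinics, flyers and a graduate newsletter, an employee of the manufacturer sends a study e-mail "to individuals who have purchased an Upright device in the past on our behalf". Recipients who are interested contact the study team. The same section shows that the product is on general sale: "When someone purchases an Upright device they are added onto their mailing listserve".

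Study Population sets two inclusion criteria (age 18 to 50; posture-related back pain) and three exclusions: a list of diagnoses, neurologic deficits, and "Currently in PT". Ownership or use of a posture device appears in neither list.

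Study Procedures randomises consented subjects to the device or to control. Controls receive posture instruction and a handout, and the study gives them the device only later: "At the end of 4 weeks participants in the control group will be given an UPRIGHT device if they continue to have pain". Baseline consists of a physical exam with medical and family history. The 4-week telephone questionnaire is "to assess their current pain level, perception of posture, and satisfaction with the device".

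The Statistical Plan says the study will "be using 30 participants, as this study had 30 subjects participating in study". It compares groups by ANOVA and says nothing about prior or concurrent device use.

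**The concern.** The comparison depends on controls being without the device until the 4-week outcome, yet one recruitment channel is aimed at people who have already bought one. An owner allocated to control may simply put it on. A control from any other source could buy one after enrolment.

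Own-device use by controls moves the two arms together. The working hypothesis is "There will be no difference in back pain score or self perception of posture between those using the UPRIGHT device", so the bias runs towards it. If use is not recorded, nobody reading a null result could say whether the device did nothing or the controls were using it. A larger sample would not remove this bias.

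**Working it through.** **Text check.** Four conditions are needed for the problem to arise:

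| Condition | Where | Finding |
|---|---|---|
| Past buyers are approached | Recruitment | Yes, explicitly |
| An eligibility rule removes owners or users | Study Population | None; current PT is the only concurrent treatment excluded |
| Owners can be allocated to control | Study Procedures | Yes; all consented subjects are randomised, with no stratification by ownership stated |
| Own use is barred or recorded | Study Procedures, Statistical Plan | Not stated; the account for device data is described within the device-group set-up |

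**Sample size.** The plan's 30 agrees with its three blocks of 10 (3 × 10 = 30). It has no power calculation to reproduce. A 1:1 ratio is not stated; I assume 15 per arm. Study Population also speaks of enrolment "with a target accrual of 35 participants treated"; for that I assume an 18/17 split.

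**Dilution, with no effect size assumed.** If k of n controls get the full device effect, the expected difference is multiplied by (1 − k/n):

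- n = 15: k = 1 gives 0.933 (6.7% lost); k = 3 gives 0.800 (20% lost); k = 5 gives 0.667 (33% lost).
- n = 17: k = 1 gives 0.941 (5.9% lost).

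**Power, illustration only.** The effect, SD, alpha and share of owners f are not in the documents. I take a two-sided 5% t-test, unit SD and a true effect of 1.06 SD, chosen because it gives 80.0% power at 15 per arm (noncentral t); at 18/17 it gives 86.0%. In the simulation each control is independently a full-effect user with probability f (all owners use the device) or f/2 (half do).

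| f | 15/15, all use | 15/15, half use | 18/17, all use | 18/17, half use |
|---|---|---|---|---|
| 10% | 69.2% | 74.7% | 76.0% | 81.3% |
| 20% | 57.6% | 69.0% | 64.5% | 76.0% |
| 30% | 45.8% | 63.2% | 52.3% | 70.5% |
| 50% | 25.9% | 51.6% | 29.8% | 58.4% |

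At f = 5% with all owners using it, power at 15/15 is about 75%. At a true effect of 0.5 SD, power is only 26% (15/15) or 30% (18/17) before any dilution, so the small sample is the larger problem there.

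**Dropping owners from the analysis.** This leaves 15 × (1 − f) per arm: 12, 10.5 and 7.5 at f = 20, 30 and 50%. At 1.06 SD, power is 69.9% with 12 per arm, 65.7% with 11, 61.1% with 10, 50.6% with 8 and 44.6% with 7. That beats the all-use case but is about level with the half-use case.

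**The case against.** **Unseen material.** The e-mail script and the questionnaire are not shown, and consent material is not part of the text reviewed. A non-use instruction or a question on own use could sit there. This limits that part of the point to what the visible text states. It does not touch eligibility: the criteria are listed under Study Population and ownership is not among them.

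**Past purchase is not current use.** A buyer may own a different model, or may have stopped using it. Anyone eligible still has back pain, and controls would lack the study's training programme, calibration and adhesives. Full effect per user is therefore best read as an upper bound. That stands, and it is why the figures are conditional. The shares f have no basis in the documents, and at 5% the loss is modest.

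**The device arm is affected too.** Prior users randomised to the device may have little left to gain. If owners there gain nothing and no control uses a device, power at 15/15 and 1.06 SD is about 57, 46 and 26% at f = 20, 30 and 50%, the same loss as in the all-use case. This adds to the concern. Excluding owners deals with it; instructing controls does not.

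**The hypothesis is a conventional null.** The stated purpose is to look for improvement, and the plan claims no equivalence. That is fair, but a null result blurred by contamination is uninformative on either reading.

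**The 35 may be 30 plus the 5 healthy pilot users.** That is possible, so the 18/17 figures are secondary.

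**Conclusion.** The concern holds. As written, the plan recruits past buyers, does not exclude them, and can randomise them to control, with no stated bar on or record of own-device use. This is a design weakness and not merely a missing detail, and it should be fixed.

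Its actual size cannot be known from the documents. What can be said is that 6.7% of the expected difference is lost for each full-effect user among 15 controls, assuming 1:1 allocation of 30. The power losses also rest on an assumed 1.06 SD effect, 5% two-sided testing and assumed owner shares. The conclusion about the text does not depend on any of these.

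**What to change.** 1. **Study Population and Recruitment.** Add a fourth exclusion criterion: owns or has used an Upright device. Ask about it at screening, before randomisation, for every recruitment source. Drop the customer mailing, since it targets people this criterion turns away.
2. **Study Procedures.** Instruct controls not to use any posture-feedback device until the week-4 assessment. In the week-4 questionnaire, ask all participants about use of any device the study did not supply. This also covers controls who buy one after enrolment.
3. **Statistical Plan, for anyone already randomised.** Keep the comparison of all randomised participants as the main result. Pre-specify a sensitivity analysis without prior owners, identified from pre-randomisation information such as screening or recruitment-source records. If ownership is known only from self-report after allocation, label the analysis exploratory: participants know their arm, and reporting may differ by arm.

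If the team keeps the mailing, stratifying by ownership would balance the arms but would not stop own-device use, so step 2 would still be needed. Neither measure would address prior users in the device arm who have little left to gain.

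The cost is one eligibility line, one screening question, one instruction and one week-4 question. Accrual may slow with the loss of one channel, although the two clinics, flyers and newsletter remain. Some lapsed users who pose little risk would be turned away, and the sensitivity analysis gives up precision.
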